3. INTERVENTION

3.1. Intervention and Comparator

The intervention aims to prevent homelessness among households identified as being at risk of homelessness, through making proactive calls to residents and signposting them to the appropriate services. These calls will be preceded by a text message from the LA to increase engagement and reduce worries about scams

amongst recipients. However, these text messages will not contain any material information and are not considered to be a part of the intervention.

The at-risk households will be identified using Xantura's predictive model, which uses LA data to generate a risk score for all households in the LA. The higher the risk score, the higher the household's (predicted) risk of becoming homeless in the next three to six months. Xantura will share a list of at-risk households with Verian for randomisation, and following randomisation, Verian will share a list of the households allocated to the treatment arm in their area with each LA, via the OneView platform.

Call handlers at the LA will contact a member of each household on the list and signpost them to support, with the aim of preventing homelessness. Our approach is intent to treat, so we do not require participants to have a phone number in order to be eligible for the trial; our sample simply reflects the information that councils hold, which may not be complete. Any household without a phone number will be marked as non-compliant. However, we note that if a large proportion of participants have no phone number then it reduces our chances of finding an effect in the primary intention to treat analysis. (Not being able to call households will depress the treatment effect, albeit in a manner that we would expect to see if the intervention was scaled up and rolled out.)

Before they make the phone call, call handlers will send the individual(s) in the household a pre-notification text message from the LA to let them know they should expect a call. The timing and content of any text message is at the LA's discretion, though a template message will be provided. When making the call, they may then refer to the pre-notification to allay any concerns about the calls being scams/fraudulent.

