5.2. Study Design

Study design details

The IE is a two-arm parallel RCT with randomisation at the household level, blocked by LA and predicted risk of homelessness. Households in the 'treatment' arm will receive proactive support (in the form of a phone call) from their LA in addition to BAU support. Households in the 'control' arm will only receive BAU support from LAs. This varies between LAs and refers to the range of activities that LAs and local organisations (including the third sector) undertake, and services they offer, to prevent and reduce homelessness. This support is available to households in both

the intervention and control arms, the difference is whether they receive a phone call that signposts them to the relevant support for them.

Allocation

Verian will randomly allocate households into the trial's two arms with equal probability, with a blocking design to ensure that the sample within each LA is as well balanced as possible on predicted risk of homelessness at the trial's start.

To assign blocks, we will independently sort each LA's sample by a continuous risk score generated by Xantura and then sequentially allocate households to blocks of four, following the sorted order. The target sample size at this point will be a multiple of four, so all blocks should be fully filled. If this is not the case, any remaining households will be entered into the final block. Once sorted into blocks, we will randomly assign households within each block so that every block of four contains two treatment households and two control. If the final block contains an odd number of households, we will randomise those households freely. The sample is thus stratified by LA and then risk score within LA.

We will randomise using the R package 'randomizr' (Coppock, 2019). One researcher will conduct the randomisation, but the code will be checked by another researcher to ensure it has been conducted correctly and can be reproduced. Once conducted, the randomisation code will be saved and made available in the OSF pre-registration that will be published for this trial.

Batching

We will deliver the sample to LAs in three batches, at the start of the first, second, and third months of the trial. We will run the randomisation separately for each batch, using up-to-date risk scores generated by Xantura.

Update to protocol: Study design in Test Valley

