6.3. Enrolment

Enrolment is automatic for selected households. We have determined that collecting informed consent for the impact evaluation would pose too great a risk to the validity of the evaluation. However, households will have the opportunity to opt out of the intervention and to opt out of their data being used in the evaluation - for more information see sections 15.2 and 16.3. Individuals in the treatment group will receive a pre-notification text message before the LA call informing them of the upcoming call and providing a link to the project's [Privacy Notice](#).

We will collect consent from any interviewees we speak to in the context of this project. Potential interview participants will be provided an information sheet and the Privacy Notice prior to them being asked if they consent to being interviewed.

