8.2. Retention strategies

Given that the recruitment and assessment processes are driven by administrative data, and that the intervention does not require ongoing compliance on behalf of the household contacted by the LA, retention is not expected to be a significant challenge in this evaluation.

In order to promote engagement with the intervention, a lead adult of each household in the intervention arm will receive a pre-notification text message alerting them to the fact that they will receive a phone call from their LA. Households in the control arm will not be notified that they are included in the trial.

There are no additional incentives offered to participants for participation in this trial.

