This definition does not consider whether household members were sent a text message because the purpose of that part of the intervention is solely to increase uptake of the calls, which is directly measured by the compliance indicator. That means a household who received the call but not the text message would still be considered fully compliant, while one who received the message but not the call would be considered non-compliant.

Our measure of compliance will be a binary indicator; set to 1 if all of the above are true, or otherwise set to 0. First, this indicator is regressed on the variable indicating random assignment to treatment at the trial's start (the instrument). The resulting model predicts treatment received based on allocation to arm, which is then substituted in the primary analysis model for the variable representing allocation to treatment.

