- **Informed consent (intervention & impact evaluation data processing):** Participants in the study will not be directly informed about the study and will not be asked to provide informed consent prior to their data being processed and randomisation. This is necessary to mitigate the risk that informing the control group of the study influences behaviour and invalidates any findings. This decision was carefully considered and alternatives explored to ensure

there were no better options that would allow for a robust evaluation. Households in the treatment group will receive a pre-notification text linking to the Privacy Notice and may be told about the study during the proactive call(s). They may withdraw from the intervention, and/or from the impact evaluation, by contacting Xantura to do so. To opt out of the intervention, they would need to do so prior to receiving the call from their LA. Participants may decline further contact during or after the call, although part of the intervention will have already been administered at this point. The information about the option to opt out of the intervention and/or the evaluation, and the process for withdrawing, can be found in the project's [Privacy Notice](#). For more information about our approach, see 16.3.

- **Informed consent (qualitative research – IPE):** Participants in the qualitative research may be contacted by their LA with informational materials about the qualitative research, and an invitation to participate. These materials will include a project information sheet, the Privacy Notice, and a consent form, and only if participants complete this consent form will Verian contact them for an interview. Verian will confirm consent to be interviewed prior to the interview commencing and will clearly communicate to participants that they may withdraw from the interview at any time, and that not consenting to an interview nor withdrawing from an interview will have any negative repercussions for them.

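### The arms differ by a text and a call, but the protocol states the contrast as the call alone, and its complier analysis counts text-only households as untreated

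*Protocol*

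**What the plan says.** **Who gets the text.** Protocol section 6.3: "Individuals in the treatment group will receive a pre-notification text message before the LA call". By the same section, the message tells them to expect the call and links to the Privacy Notice. Of the other arm, section 8.2 says: "Households in the control arm will not be notified that they are included in the trial".

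**What the text is held to be.** Section 3.1: "these text messages will not contain any material information and are not considered to be a part of the intervention". The same section adds: "The timing and content of any text message is at the LA's discretion, though a template message will be provided". The TIDieR table (Table 4) repeats that the text lies outside the intervention. Section 10.6, explaining why the text is left out of the compliance definition, describes it as a part of the intervention whose only purpose is to raise call uptake.

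**What is said to differ between arms.** Section 2.1 says the groups differ in whether the local authority (LA) telephones them. Section 5.2, having noted that usual support is open to both arms, says: "the difference is whether they receive a phone call that signposts them to the relevant support for them".

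**How the complier analysis treats the text.** Section 10.6 plans a complier average causal effect (CACE) by two-stage least squares (2SLS), with allocation as the instrument. Compliance means a completed call made before any homelessness application, and "one who received the message but not the call would be considered non-compliant".

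**The concern.** By design the arms differ in two things, and the protocol names only one of them as the contrast. Two consequences follow.

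First, the primary result would be reported as the effect of a proactive call when what was randomised was a text followed by a call attempt. An LA deciding what to adopt needs to know that the estimate belongs to the package.

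Second, the instrumental-variable analysis needs allocation to affect the outcome only through a completed call (the exclusion restriction). A treatment household that was texted but never reached has been exposed to something that no control household received, yet it enters as untreated. If the text has any effect of its own, 2SLS loads that effect onto the households that completed a call.

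Section 10.6 rests the exclusion of the text on its purpose. A purpose of raising uptake does not show that there is no other effect. Nor is the claim of no material information secured, because LAs decide the content. Section 15.2 adds that the linked notice is where households learn how to opt out.

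**Working it through.** **1. The plan's own figure, for scale.** Section 9 gives a minimum detectable effect of 2–7 percentage points (pp) for Scenario C (achieved n = 1,600, so 800 per arm; two-sided 0.05, power 0.8). A two-proportion calculation with pooled variance gives 1.97pp at a control rate of 3% and 6.98pp at 50%, which matches. The 3% end is an assumption, because Figure 3 is not visible. This figure concerns the intention-to-treat (ITT) effect. The text issue does not alter it.

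**2. Formulas.** On the risk-difference scale, let c be the share of the treatment arm that is compliant, t the share texted, and d the direct effect of the text (the part that does not run through a completed call). No control household is called or texted.

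- ITT = c × (call effect) + t × d
- 2SLS estimate = ITT / c = (call effect) + (t / c) × d
- Shift in the CACE = (t / c) × d

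**3. Inputs.** The documents give no value for d, so 0.5, 1 and 2pp are assumed. They give no expected compliance either. Section 1.1 reports an earlier Barking and Dagenham outreach in which 68 of 210 targeted residents were reached: 68/210 = 0.324. That serves as a low illustration, with 50% and 70% as assumed alternatives. The share texted is set at 100%, then at 80%.

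**4. Results: shift in the CACE, in pp.**

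| Compliance c | d = 0.5, t = 100% | d = 1, t = 100% | d = 2, t = 100% | d = 1, t = 80% |
|---|---|---|---|---|
| 32% | 1.54 | 3.09 | 6.18 | 2.47 |
| 50% | 1.00 | 2.00 | 4.00 | 1.60 |
| 70% | 0.71 | 1.43 | 2.86 | 1.14 |

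For example, at 32% with d = 1: 1 / 0.324 = 3.09. Of this, 1pp is the text's effect in the called households themselves, and 0.676 / 0.324 = 2.09pp comes from text-only households. At 70% the split is 1 + 0.30 / 0.70 = 1.43.

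**5. Effect on the primary test.** With no call effect, 800 per arm, everyone texted and d = 1pp, a significant benefit would appear in 5.9% of trials at a control rate of 50%, 6.4% at 30% and 10.1% at 10%, against 2.5% in that direction under a true null. Leaving Test Valley out of the primary model, as section 5.2 now provides, reduces n and brings these rates nearer to 2.5%. A small text effect therefore hardly moves the ITT test. Dividing by c scales the standard error of the CACE as well, so the distortion lies in the size quoted for a completed call rather than in its significance.

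**The case against.** **The text is disclosed and reasoned about.** Section 3.1 gives its purpose (engagement and reassurance about scams), Table 4 lists it under procedures and mode of delivery, section 10.6 explains its omission from compliance, and section 11.2 records its sending with a time stamp. This stands, and an attentive reader would know that a text preceded the call. It does not reconcile the sections that disagree on whether the text belongs to the intervention.

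**A reader might infer that the ITT is biased.** It is not. It validly estimates the effect of allocation to text plus call, and uptake raised by the text is a legitimate route to benefit. On the primary analysis the fault lies only in how the contrast and conclusion are worded.

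**A reader might infer that the protocol itself says informing households changes behaviour.** It does not. Section 15.2, on not informing participants, says: "This is necessary to mitigate the risk that informing the control group of the study influences behaviour and invalidates any findings". Section 16.3 says that telling controls they were identified as at risk might invalidate the results. Both describe a possibility, and both concern telling controls about the study or their risk status. Nothing shows that the text discloses risk status, and the Privacy Notice is not among the documents. These passages are a reason not to take the text's inertness for granted; they are not evidence of an effect.

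**Instrument assumptions are commonly set out in the analysis plan.** Agreed, and the absence of a formal statement is not the point. The protocol already fixes the coding of text-only households and gives a reason that does not support it.

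**The figures are hypothetical.** Also true. The 68/210 comes from Council Tax summons-stage calls, whereas this trial makes three to five repeat attempts. Households without a phone number cannot be texted, and section 16.3 treats sending as optional for LAs, so t may fall short of 100%.

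**Conclusion.** The protocol states the between-arm contrast wrongly, as the call alone, and contradicts itself on whether the text is part of the intervention. The primary ITT analysis needs no change beyond its label: the conclusion belongs to the package of text plus call.

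The CACE is valid for the call only if the text has no effect except through a completed call, and the stated purpose of the text does not establish that. If the assumption fails, the direct text effect enters multiplied by t/c: for an assumed 1pp with all treatment households texted, about 3.1pp at 32% compliance and 1.4pp at 70%. Those figures rest on assumed values of the text effect, the share texted and compliance, and on the linear risk-difference scale. They show sensitivity, not a known bias. The true direct effect may be zero, in which case only the wording needs correcting. The point is worth settling before analysis but does not threaten the trial's main result.

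**What to change.** 1. In sections 2.1, 3.1, 5.2 and 10.6 and in Table 4, define the treatment as *pre-notification text plus proactive call*, and remove the statements that place the text outside it, so that all five places agree.
2. State the primary conclusion for that package.
3. In section 10.6, state that the CACE assumes the text affects the outcome only through a completed call, in place of the argument from its purpose. Report the adjusted estimate (ITT − t × d) / c over a range of assumed d, for instance 0, 0.5, 1 and 2pp, taking t from the text-sent field that section 11.2 already collects and c from the call records.
4. A 2SLS run that counts receipt as either a text sent or a call completed may be added only if it is labelled as the effect of receiving the package. As the share texted nears 100% it moves towards the ITT, so it cannot separate the text from the call.

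The cost is wording in five places and one small sensitivity analysis on data already recorded. No change to sample size or delivery follows. The claim becomes slightly less specific, a package rather than a call. Section 13.2 provides for an addendum before analysis, which Table 5 schedules from May 2026.
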